4.5.1 Whole body PET/CT

A whole body PET/CT will be performed beginning 1 hour post ^{18}F NaF injection.

Good hydration is recommended in order to reduce excessive radiation exposure. The patient should void one-half hour after the administration of ^{18}F NaF Injection and as frequently thereafter as possible.

CC Protocol Number: 14-C-0140
Abbreviated Title: DCFBC in prostate cancer
Version date: 10/27/2015
CIP #: 9622

4.6 Additional Imaging

1. For subjects with known metastatic disease (Arm 3), additional Na¹⁸F PET/CT and ¹⁸F DCFBC PET/CT will be performed, within 3 weeks of each other and within 4-6 months following the initial scans.

2. Additional PET/MR imaging may be done if scheduling allows, and the subject does not have any MR incompatible conditions or implants) immediately after F18 DCFBC PET/CT in all arms to explore visibility of anatomic correlates to tracer uptake between the two modalities. No additional radiation risk is involved.

Patients who will undergo additional PET/MR will first complete the PET/CT portion in the Molecular Imaging Clinic (MIC). They will then be escorted to the Clinical Center Radiology Department for PET/MR imaging. Arm 2 patients with urinary catheters will have them removed prior to leaving MIC.

MRI image acquisition will follow with sequences acquired with standard MRI imaging in order to spatially correlate findings, which may include T2W, diffusion, and MRSI. Simultaneous PET emission data will be acquired with MRI images. This portion of the study will last approximately 1 hour. MR contrast will not be used to this portion of the visit, and no additional radiotracer will be injected.

4.7 Pathology

4.7.1 Surgical Pathology (Standard of care, for ARM 1 only)

Specimens will undergo standard preparation and sectioning in the Department of Surgical Pathology for pathological diagnosis. Additional sectioning and IHC staining may also be conducted by an approved outside pathology laboratory. Prostatectomy specimens will be processed by patient specific MRI based specimen molds to provide geometric and spatial alignment between MRI, PET and histopathology. The specimen results will be correlated with ¹⁸F DCFBC PET/CT results and MRI imaging results.

4.8 Biopsy

Biopsy of abnormal sites of uptake will not be required by this protocol; however if a suspicious focus of uptake is identified, this information will be communicated to the referring physician, who may choose to evaluate the site further with biopsy or clinical follow-up. In such a case any follow-up information obtained (including pathology) will be collected as clinically needed.

4.9 Correlative Studies

4.9.1 Imaging Correlation

A volume of interest (VOI) will be drawn over the target lesion on the PET/CT and PET/MRI (if PET /MRI is obtained) images for each subject and Standard Uptake Values (SUVs) will

CC Protocol Number: 14-C-0140
Abbreviated Title: DCFBC in prostate cancer
Version date: 10/27/2015
CIP #: 9622

be recorded. Focal areas of abnormal uptake will be compared with any abnormalities on standard of care imaging.

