2.3 Rationale

We propose to further expand upon initial clinical work with ^{18}F DCFBC and evaluate its usefulness in three different categories of prostate cancer- localized, metastatic and biochemical recurrence. In the case of localized disease ^{18}F DCFBC distribution will be compared with endorectal coil multiparametric MRI at 3T. In the case of potentially recurrent or metastatic disease ^{18}F DCFBC will be compared with CT, bone scan and/or Sodium Fluoride PET/CT bone scan. This study should offer insights into how and when ^{18}F DCFBC could be used in the clinical setting to direct proper management. Moreover, by monitoring ^{18}F DCFBC uptake in metastatic disease over time, one may better understand how useful this agent may be in monitoring responses to therapy.

Amendment C Addendum:

The agent has shown some preliminary promising results. In Arm 2, we have had patients with questionable uptake only near the bladder. We have noted that bladder activity may obscure possible prostate bed recurrence, so a recent amendment was approved for urinary catheterization with possible bladder irrigation. We have only been able to scan a limited

CC Protocol Number: 14-C-0140
Abbreviated Title: DCFBC in prostate cancer
Version date: 10/27/2015
CIP #: 9622

number of patients using this technique and have been able to locate areas suspicious for recurrence in some. Additional patients will help to determine if the technique is beneficial in visualization, potentially improving detection rates for early local recurrence. In Arm 3, we have noted a mixed response in tracer uptake for hormone sensitive patients, which contradicts what other PSMA research groups are reporting. They assert that uptake is always positive in patients on anti-androgen treatment. Our findings could be due to the heterogeneous evolution of lesions to castrate resistance, but currently our numbers are small. More patients to this arm will allow better characterization of the relationship between 18F DCFBC uptake and androgen deprivation therapy.

Amendment E Addendum:

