12.1.3 Imaging Data

Extracted imaging data include:

- (1) PET imaging data will include SUV for each region of interest
- (2) All image data will be stored on a secure server, with access limited to credentialed users. This will permit flexible numeric raw data extraction for quantitative analysis and creation of summary data reports.

CC Protocol Number: 14-C-0140
Abbreviated Title: DCFBC in prostate cancer
Version date: 10/27/2015
CIP #: 9622

- (3) Anonymized image data from this study will be stored in a secure database that it is administered by the Cancer Imaging Program, NCI. The data may be shared with research collaborators to improve upon current methods of image analysis. The database is password protected and access is only given to qualifying collaborators.

Imaging findings for Na¹⁸F PET/CT will be dictated into the PACS system similar to other clinical radiologic studies, but dictations for ¹⁸F DCFBC PET/CT will only reflect the radiotracer dose, injection site and a statement indicating that the scan is for research purposes only.

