14.2 Secondary Analysis

For patients with localized disease, the diagnostic accuracy of ^{18}F -DCFBC PET/CT will be compared with multiparametric MRI using the sector-based analysis. Patient-specific sensitivity and specificity will be estimated and differences in sensitivity and specificity between different modalities will be tested by the Wilcoxon signed-rank test. Change of ^{18}F -DCFBC uptake for patients with metastatic disease over time will be estimated by the linear mixed effect model where random intercept will be used to account for the intra-patient correlation of longitudinal ^{18}F -DCFBC uptake. In addition, in patients with metastatic prostate cancer to bone, the uptake of ^{18}F -DCFBC will be correlated with the uptake of the emerging gold standard, ^{18}F Sodium Fluoride PET/CT by the Spearman rank correlation.

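### Arm 3 change in uptake: the plan does not settle which lesions are measured, and its only change model has no lesion-level component and no ADT term

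*Combined protocol and SAP*

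**What the plan says.** **What is measured.** Section 4.9.1 (Imaging Correlation), written for all arms, says that a VOI "will be drawn over the target lesion on the PET/CT and PET/MRI (if PET /MRI is obtained) images for each subject" and that SUVs are recorded. Target lesion is not defined: there is no number, no selection rule and no rule for matching lesions between sessions. The next sentence is in the plural: "Focal areas of abnormal uptake will be compared with any abnormalities on standard of care imaging". Section 12.1.3 (Imaging Data) says "PET imaging data will include SUV for each region of interest", and adds of the stored images: "This will permit flexible numeric raw data extraction for quantitative analysis and creation of summary data reports".

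**How change is analysed.** Section 14.2 says that change in DCFBC "uptake for patients with metastatic disease over time will be estimated by the linear mixed effect model", in which a "random intercept will be used to account for the intra-patient correlation of longitudinal" uptake. It names no lesion term, no random change and no covariate.

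**What the analysis is for.** Section 1.2 sets a secondary objective on change in DCFBC distribution at 4-6 months in metastatic disease and gives the effect of ADT as its example. Section 4.1 has changes in distribution compared with clinical data and imaging, without a method. The Amendment C addendum in section 2.3 says "In Arm 3, we have noted a mixed response in tracer uptake for hormone sensitive patients" and then "Our findings could be due to the heterogeneous evolution of lesions to castrate resistance, but currently our numbers are small". It asks for more Arm 3 patients in order to characterise better how uptake relates to ADT.

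**The concern.** The reason for enlarging Arm 3 has two parts: a mixed response that may arise at lesion level, and the relation of uptake to ADT. The planned analysis addresses neither. A model that estimates one average change lets rising and falling uptake offset each other, and a model without treatment status cannot relate change to treatment. The choice of lesions is also left open. It could therefore be made after both scans have been seen, when it can shape the result.

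At stake is a secondary objective, but it is the one for which the arm was expanded. If the plan is followed as written, the extra men and their second scans would yield an average change and no pre-specified answer to the question asked.

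**Working it through.** **1. The plan's own Arm 3 figure.** Section 14.1 gives a 90% interval of (0.54, 0.86) for 20 patients, mean concordance 70%, SD 43%. Check: 0.70 ± 1.645 × 0.43/√20 = 0.70 ± 0.158 = (0.542, 0.858). It reproduces, but it concerns concordance with conventional imaging. The plan states no precision for change in uptake.

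**2. The two readings of the measured unit.**
- One lesion per man (4.9.1 read literally): the spread of change between lesions within a man cannot be estimated.
- Several lesions per man (12.1.3): the data exist, but section 14.2 specifies no output that uses them by lesion.

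Several lesions are to be expected. Section 14.1 reports 32 sites in five patients of the cited study, 2 to 12 per patient, mean 32/5 = 6.4.

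**3. Offsetting.** Let a share p of lesions rise by d and the rest fall by d (assumed). The mean change is p·d − (1−p)·d = (2p−1)·d.
- p = 0.5: 0
- p = 0.7: 0.4d
- p = 0.3: −0.4d

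So the offset is complete only in the balanced case and partial otherwise. The same arithmetic applies if whole men, rather than lesions, move in opposite directions.

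**4. The model in 14.2 on simulated data.** All values are assumed: 20 patients, two scans, 60 replicates, log SUV, patient SD 0.4, lesion SD 0.3, error SD 0.12. Lesion changes are either zero, or +0.5 or −0.5 with equal chance.

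| Lesions per man | True lesion change | Mean estimated change (SD over replicates) | Residual SD | Within-patient SD of lesion change |
|---|---|---|---|---|
| 1 | none | 0.003 (0.037) | 0.123 | not estimable |
| 1 | ±0.5 | 0.008 (0.117) | 0.376 | not estimable |
| 5 | none | 0.001 (0.019) | 0.298 | 0.166 |
| 5 | ±0.5 | 0.003 (0.057) | 0.47 | 0.528 |

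The estimated mean change does not separate opposing changes from no change. With five lesions, the within-patient SD of lesion change does (0.53 against 0.17), but nothing in the plan reports it. The residual SD also rises, but it mixes differences between lesions with differences in change and is not a planned output.

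**5. Chance of seeing a mixed response.** If lesions within a man move independently and a share p rise, the chance of at least one riser and one faller among k lesions is 1 − p^k − (1−p)^k.

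| k | p = 0.5 | p = 0.3 | p = 0.2 |
|---|---|---|---|
| 1 | 0 | 0 | 0 |
| 2 | 0.50 | 0.42 | 0.32 |
| 5 | 0.94 | 0.83 | 0.67 |
| 12 | >0.99 | 0.99 | 0.93 |

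Neither p nor independence comes from the documents. The table shows only that the number of lesions measured matters.

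**6. ADT.** Section 1.2 and the Amendment C addendum both name ADT. The Précis says that Arm 3 men may or may not be on therapy, and that treatment in the imaging interval must be on record. Treatment status will therefore vary and be known, yet section 14.2 does not use it.

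**The case against.** The case on the other side is substantial, and it rules out several stronger readings.

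- **Only one lesion per man is measured.** A reader might infer this from 4.9.1. The text does not say one, the sentence covers every arm and optional PET/MRI, and 12.1.3 points to several. What stands is that the two sections disagree.
- **The mixed response is within patients.** The addendum does not say so. It speaks of hormone-sensitive patients and contrasts its finding with other groups' claim of universal positivity, which could be a difference between men. Lesion evolution is offered only as a possible cause. The gap remains either way, because a random intercept with no treatment term does not describe men changing in different directions.
- **The effect cannot be seen at all.** Whole-body images from both sessions are stored for further extraction, and section 4.1 compares changes in distribution. What is missing is a specified analysis, not the data.
- **A heterogeneous response would be reported as no change.** That needs rises and falls balanced in number and size.
- **The measured lesion would fall by regression to the mean.** This applies only if lesions are chosen for high baseline DCFBC uptake. No section says that they are, although none excludes it.
- **The mixed-response probabilities are high.** They assume independent lesions. Positive correlation within a man under shared systemic therapy would lower them.

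It is also fair to say that this is a secondary analysis in a pilot study, where some flexibility is usual.

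**Conclusion.** The point holds as a gap in specification. Sections 4.9.1 and 12.1.3 do not agree on which lesions are measured. The single planned analysis of Arm 3 change estimates an average, with no lesion-level component and no ADT or hormone-status term. Followed as written, rises and falls offset partly or wholly, and no planned analysis shows the mixed response or the relation of uptake to ADT. Later work on the stored images would be unplanned.

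The size cannot be fixed from the documents, which give no lesion-level changes. The offsetting figures, the simulation and the mixed-response probabilities are illustrations on assumed inputs. The conclusion itself rests only on the wording of the sections and on the model estimating a mean. The primary concordance analysis is not affected. The change is worth making because it concerns the stated reason for enlarging the arm and needs no new scans or patients.

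**What to change.** **Measurement (4.9.1 and 12.1.3, Arm 3).** Reconcile the two sections. At baseline, list all measurable lesions, or up to a fixed number per man, from conventional and NaF imaging and not by DCFBC uptake. Draw a VOI on those same lesions at both sessions, at one stated post-injection time point.

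**Analysis (14.2).**
- Add hormone/ADT status to the mixed model.
- Add a lesion-within-patient term, or a random change. A random change by patient needs several lesions per man. With one VOI per lesion per session, variation in change between lesions stays in the residual, so the next item is needed as well.
- Report per patient, by hormone status, the proportion of lesions rising and falling beyond a percentage set in advance, alongside the mean change. The documents give no SUV repeatability figure, so none is suggested here.

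**Cost.** Wording, plus more VOI drawing on scans already in the plan. With 20 men, two sessions and 2 to 12 lesions each, the count is 20 × 2 × 2 = 80 to 20 × 2 × 12 = 480 VOIs. It doubles to 160 to 960 if both the 1-hour and 2-hour scans are measured. Sections 14.1 and 14.3 already need site-level findings per patient from conventional imaging, so much of the baseline list will exist, and interval treatment must already be on record.

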4.9.2 Pathologic and Imaging Correlation

NIH Clinical Center prostatectomy or standard of care biopsy is planned for subjects enrolled in ARM 1 (localized disease). The specimen results will be correlated with ¹⁸F DCFBC PET/CT and MRI results.

Following radical prostatectomy, surgical specimens will undergo standard preparation and sectioning in the Department of Surgical Pathology for pathological diagnosis. Urologists from the UOB at the NIH Clinical Center have extensive experience with laparoscopic prostatectomy. The surgical specimen obtained with the laparoscopic procedure is preserved at least as intact as in open laparotomy procedures. To date, the UOB has performed over 250 MRI/pathology correlations after laparoscopic prostatectomies.

At resection, the specimen is painted with three different colored inks (anterior right with blue, anterior left with red and urethral side with yellow) for correct orientation, and the gland is left to dry for 1-2 minutes. The gland is divided into two equal parts in the axial plane; from one of these parts, a rectangular sample of 2x1x0.2 cm is taken for DNA analysis – it is understood that this sample may contain cancer tissue and may not be reported. The DNA analysis is for research interest of the NCI and is not a component of this protocol. The two cut parts are re-glued for fixation. Fresh prostate gland is hard to hold and cut, so slicing after fixation is better and easier. The glued and combined gland is kept in formalin for 24 to 48 hours at room temperature for fixation. After fixation, the seminal vesicles are removed and then the gland is sliced via a custom-made mold based on the 3D imaging information from high resolution T2W MR images. The molds are equipped with slots spaced 6 mm apart. The gland only shrinks by approximately 3% after the first fixation and prior to slicing. A single-blade steel knife is used for one prostate. In this manner, attempts will be made to cut the specimens in the same plane as the imaging was performed. The sliced gland is kept within formalin for as long as a week at room temperature. The tissue is processed into paraffin blocks and sectioned by standard methods. The gland shrinks by 10-15% after all of these procedures.

Slide specimens will be stained for morphology and regions with malignant tumor, non-malignant pathologies, and normal tissue will be marked by the pathologist. The resultant pathologic specimen is cut transversely using the same alignment as the T2W MR images. Thus, the MRI and PET/CT scans are approximately aligned with the prostate specimens.

Tumor extent, Gleason Score and presence of BPH, and inflammation on tissue sections will be evaluated and correlated with uptake of ¹⁸F DCFBC.

CC Protocol Number: 14-C-0140
Abbreviated Title: DCFBC in prostate cancer
Version date: 10/27/2015
CIP #: 9622

4.9.3 PET: MR comparison (Arm 1 or other MR available)

The distribution of uptake of ^{18}F DCFBC depicted by PET/CT will be compared with tumor indicators observed on the MR image data (T2W MRI, DCE MRI, MR DWI, and MRSI) on a per-subject and per-lesion basis.

In case the new imaging agent shows an unexpected finding, this may be correlated with conventional imaging.

4.10 Off-Study Criteria

In cases where a subject withdraws or is withdrawn from the study after administration of ^{18}F DCFBC and before surgery or biopsy is performed, a replacement subject will be enrolled.

Should a subject withdraw after administration of ^{18}F DCFBC, or should the investigators decide to withdraw the subject, all efforts will be made to complete and report the protocol-stipulated observations up to the time of withdrawal as thoroughly as possible. A final evaluation at the time of the subject's withdrawal should be made and an explanation given of why the subject is withdrawing or being withdrawn from the study. The reason and date and time of withdrawal must be recorded. If the reason for withdrawal is a clinical AE, monitoring will continue until the outcome or stabilization is established.

Patients will be taken off treatment upon completion of all study procedures. The patients will be taken off study one year after the follow-up period. During this one year time period, the patient's PSA levels and prostate cancer related medical history, biopsy results, imaging studies and will be collected.

4.10.1 Criteria for Removal from Protocol

- Investigators have the right to withdraw subjects from the study in the event of illness, AEs, or other reasons concerning the health or well-being of the subject, or in the case of lack of co-operation.
- Subject completes a one year follow-up period upon completion of all study procedures
- Subjects can be taken off study at the discretion of the Investigator.
- Patient requests to be taken off study
- Patient non-compliance with protocol guidelines
- A serious or intolerable adverse event related to the study drug occurs
- Patient may not be taken off study until intolerable adverse event has stabilized or resolved.

4.10.2 Off-Study Procedure

Authorized staff must notify Central Registration Office (CRO) when a subject is taken off-study. An off-study form from the web site

CC Protocol Number: 14-C-0140
Abbreviated Title: DCFBC in prostate cancer
Version date: 10/27/2015
CIP #: 9622

(<http://home.ccr.cancer.gov/intra/eligibility/welcome.htm>) main page must be completed and faxed to [contact].

4.11 Follow-up

All subjects will be contacted by phone ~1-3 days post injection and will be asked a non-leading question to determine whether any new AEs have occurred and to follow up on any ongoing AEs since completion of PET imaging. If the patient is being evaluated in person 24 hours post-injection then a phone call will not be necessary.

Within 4-6 months following PET imaging the clinically indicated surgery or biopsy procedure will be performed.

5 Dose Modifications

Due to potential unpredictable delays and the short half-life of ^{18}F , the total dose of ^{18}F DCFBC administered may be reduced at the discretion of the principal investigator or her designee.

6 ADVERSE EVENTS: LIST AND REPORTING REQUIREMENTS

Adverse event (AE) monitoring and reporting is a routine part of every clinical trial. The following list of AEs (Section 6.1) and the characteristics of an observed AE (Section 6.1.1.1) will determine whether the event requires expedited reporting (via CTEP-AERS) **in addition** to routine reporting.

6.1 Comprehensive Adverse Events and Potential Risks List (CAEPR)

The Comprehensive Adverse Event and Potential Risks list (CAEPR) provides a single list of reported and/or potential adverse events (AE) associated with an agent using a uniform presentation of events by body system. In addition to the comprehensive list, a subset of AEs, the Specific Protocol Exceptions to Expedited Reporting (SPEER), appears in a separate column and is identified with **bold** and *italicized* text. The SPEER is a list of events that are protocol-specific exceptions to expedited reporting to NCI via CTEP-AERS (except as noted below). Refer to the 'CTEP, NCI Guidelines: Adverse Event Reporting Requirements' http://ctep.cancer.gov/protocolDevelopment/adverse_effects.htm for further clarification.

NOTE: The highest grade currently reported is noted in parentheses next to the AE in the SPEER. Report **ONLY** AEs higher than this grade expeditiously via CTEP-AERS. If this CAEPR is part of a combination protocol using multiple investigational agents and has an AE listed on different SPEERs, use the lower of the grades to determine if expedited reporting is required.

Please note that a CAEPR has not been developed for ^{18}F DCFBC to-date. However, once available, the protocol will be updated to include this information.

